4.2 SCIENTIFIC RATIONALE FOR STUDY DESIGN

The trial will utilize response adaptive randomization (RAR) to favor the better performing experimental arms. Also, using RAR (being able to change how we assign subjects to the groups during the study based on information gained during the study) allows for substantially smaller sample size and provides better conclusions about the most effective treatment because it allows the study to stop early if strong results or futility are identified before the scheduled end of the study. Safety of the trial will be carefully assessed including a statistical analysis of the SAEs. This study, in addition to identifying the optimal dose, offers the opportunity to explore the treatment effect and other important outcome domains using ICP, TIL scores and brain tissue PO2. These analyses will allow us to further support a go/no-go decision regarding a subsequent definitive efficacy trial.

4.3 JUSTIFICATION FOR DOSE

Preclinical investigators working with TBI models and hyperoxia have used pressures varying from 1.0 to 3.0 atmospheres absolute (ATA). Clinical investigators have used pressures varying from 1.0 to 2.5 ATA. However, the lungs in severe TBI subjects have frequently been compromised by direct lung injury and/or acquired ventilator associated pneumonia and are very susceptible to oxygen (O2) toxicity. Working within those constraints, it is essential to determine the most effective hyperoxia dose schedule without producing O2 toxicity and clinical complications. This proposed clinical trial is designed to answer these questions and to provide important data to plan a definitive efficacy trial.

4.4 END OF STUDY DEFINITION

A participant is considered to have completed the study if he or she has completed all phases of the study including the last visit or the last scheduled procedure shown in the Data Collection Schedule, withdraws consent, or dies. Section 1.3.

5 STUDY POPULATION

5.1 INCLUSION CRITERIA

- Age 16-65 years
- Severe TBI, defined as an index GCS (iGCS) of 3 to 8 (if intubated, motor score<6) in the absence of paralytic medication
- For patients with a GCS of 7 or 8 or motor score = 5, Marshall computerized tomography (CT) score >1
- For patients with an alcohol level >200 mg/dl, Marshall computerized tomography (CT) score >1
- For patients not requiring a craniotomy/craniectomy or any other major surgical procedure, the first hyperbaric oxygen treatment can be initiated within 8 hours of arrival at enrolling hospital
- For patients requiring a craniotomy/craniectomy or major surgical procedure, the first hyperbaric oxygen treatment can be initiated within 14 hours of **arrival at** enrolling hospital
- Written, informed consent from LAR or eligible for exception from informed consent

5.2 EXCLUSION CRITERIA

Criteria	Metric	Rationale
First hyperbaric oxygen treatment cannot be initiated within 24 hours of injury	Time to first hyperbaric oxygen treatment	Subjects treated >24 hours are unlikely to benefit
GCS of 3 with mid-position and non-reactive pupils bilaterally (4mm) in the absence of paralytic medication	GCS	Avoid enrolling futile cases.
Penetrating head injury	Clinician exam	Avoid enrolling subjects with very poor prognosis
Pregnant	For women of childbearing age, pregnancy will be assessed either by urine or serum pregnancy test	The effect of hyperbaric oxygen treatment on unborn fetus is unknownchallenge

Prisoner or ward of the state	Documentation of same	Challenges to conducting follow up assessments
Acute spinal cord injury with neurologic deficits.	Clinical exam	Contraindication to transporting subject to chamber. Additionally prior spinal cord injury with paralysis is a confounder for outcome assessment
Contraindication to ICP monitor placement	Clinician determination	ICP monitoring is important to delivering effective care
Pulmonary dysfunction	PaO2/FiO2 ratio≤200 using no more than 10 cm of H20 of PEEP	Risk of worsening pulmonary toxicity from hyperbaric oxygen treatment
Coma suspected to be due to primarily non-TBI causes	Clinical exam	TBI may not be the primary explanation for subject's mental status
Non-survivable injury (e.g. withdrawal of care prior to randomization, no intention for aggressive intervention, on hospice or Do Not Resuscitate (DNR) order, etc.)	Clinician determination	Poor prognosis
Concern for inability to follow- up at 6 months	Available history indicative that the subject will be inaccessible at the time of outcome determination.	High likelihood of being lost to follow-up at 6 months resulting in missing data.
Inability to perform activities of daily living (ADL) without assistance prior to injury	Clinician determination	Difficulties with ascertaining outcomes
Implantable device/drug that is incompatible with HBO treatment	Refer to manual of procedures for list of potential devices	Device may malfunction in hyperbaric chamber

Non-English Speaking Subjects

There is no exclusion based on language. We recognize, however, that several issues arise when including non-English speaking subjects. These include challenges with obtaining informed consent, and barriers to family interaction, subject tracking, follow-up, and outcomes assessment. As eligible subjects

for this study cannot consent for themselves, informed consent will be sought from an English-speaking LAR or using an IRB-approved informed consent process for non-English speaking LARs. Interactions with the family during the course of the study may require translation services. Tracking and follow up will be more difficult. Translation services will also be needed for phone and in-person follow-up. One of the most important issues will be the outcomes assessment. Fortunately, the primary outcome (GOSE at 6 month), is language-and culture-neutral, and can be assessed with a translator.

5.3 SCREEN FAILURES

The purpose of tracking screen failures is to characterize the population of TBI patients that are not enrolled in the study at participating. A minimal set of screen failure information is required to ensure transparent reporting of screen failure participants, to meet the Consolidated Standards of Reporting Trials (CONSORT) publishing requirements and to respond to queries from regulatory authorities. Minimal information includes demographics and reason(s) for exclusion.

5.4 STRATEGIES FOR RECRUITMENT AND RETENTION

Identifying and Recruiting Candidates. Potential subjects for this trial will be recruited from subjects 16-65 years of age, with a severe TBI, presenting within 24 hours of injury to the clinical sites participating in this trial. All participating clinical sites are staffed by trained research personnel capable of performing careful screening of each potential subject according to the inclusion/exclusion criteria described above.

Anticipated accrual rate: 1.6 subjects per week

Source of participants: Hospital emergency departments and intensive care units

How potential participants will be identified and approached: Trained research coordinators will monitor all trauma presentations for eligible subjects. They will be asked to inform clinical site PI and his/her team of potentially eligible participants. Age will be documented via past medical records, driver's license or learner's permit, school ID, or family member. The subject's legally authorized representative will be approached for informed consent. Subjects for whom a legally authorized representative is not available within 6 hours of arrival may be enrolled with exception from informed consent.

See section 10.1.1 for information on informed consent procedures and exception from informed consent.

5.5 PRE-TREATMENT EVALUATION

Index GCS (iGCS)

At the time of randomization in WebDCU[™], the enrolling investigator determines the subject's iGCS. The iGCS is post resuscitation, meaning oxygenation and blood pressure have been adequately stabilized. Administered short-acting sedative (propofol etc) and/or paralytics (succinylcholine) would be given time for resolution of drug effect prior to assessing the iGCS. The iGCS does not have to be performed by the study investigator. Since potential subjects will be intubated, motor score can be used for assessment and corresponds to the iGCS listed in the table below for the purpose of this study. The GCS should always be explicitly measured and should never be estimated from casual observation.

iGCS	Corresponding Motor Score	
3 - 5	1 - 3	
6 - 8	4 - 5	

Age

Age is necessary for randomization. Age should ideally be obtained from objective documentation, such as a driver's license, other formal identification, or official records. Subject, family or acquaintances can provide age in circumstances where objective documentation is not available.

6 STUDY INTERVENTION

6.1 STUDY INTERVENTION(S) ADMINISTRATION

6.1.1 STUDY INTERVENTION DESCRIPTION

The study interventions will be hyperbaric oxygen with or without additional normobaric hyperoxia or normobaric hyperoxia alone (NBH), or routine care (no hyperoxia). Hyperbaric oxygen therapy consists of breathing 100% oxygen (hyperoxia) while under increased atmospheric pressure.

6.1.2 DOSING AND ADMINISTRATION

HBO Treatments

If the subject meets inclusion criteria, has no exclusions and informed consent is obtained or is enrolled with exception from informed consent, they will be randomized to either one of six HBO treatment paradigms, one NBH treatment paradigm, or the control group. Oxygen toxicity unit (OTU) is a means of quantifying the amount of O2 exposure to the subject based on duration and pressure. Despite its name, OTU is not actually a measure of oxygen toxicity. For the purposes of this study, OTUs will be used as a measure of oxygen dose. The OTUs for the different treatment groups are listed in the table below.

Tre	atment	Oxygen toxicity Unit (OTU)
1.	1.5 ATA 60 minutes twice a day	130 x 2 = 260
2.	2.0 ATA 60 minutes twice a day	208 x 2 = 416
3.	NBH (100% O2 at 1.0 ATA) 4.5 hours twice a day	270 x 2 = 540
4.	2.5 ATA 60 minutes twice a day	296 x 2 = 592
5.	1.5 ATA 60 minutes with 3 hours of NBH twice a day	310 x 2 = 620
6.	2.0 ATA 60 minutes with 3 hours of NBH twice a day	388 x 2 = 776
7.	2.5 ATA 60 minutes with 3 hours of NBH twice a day	476 x 2 = 952
8.	Control (no hyperoxia treatment)	

For subjects receiving HBO treatment, bilateral myringotomies will be performed prior to the first treatment. For all randomized subjects, ICP will be monitored during HBO treatments and ICP will be recorded every 15 minutes. Brain tissue PO2is optional. Brain tissue PO2 values should be recorded every 15 minutes during HBO treatment HBO treatments will be delivered in both monoplace and multiplace chambers. Compression and decompression will occur at a standard 2 feet per minute. Total compression/decompression time for 2.5 ATA is 50 minutes, for 2.0 ATA is 33 minutes, and for 1.5 ATA is 16.5 minutes. Each treatment will be for 60 minutes at the specified pressure. NBH will consist of the subject breathing 100% O2 for 3 hours following HBO decompression which will be continued in the ICU. The NBH without HBO treatment arm will likewise be ventilated with 100% O2 for 4.5 hours at 1.0 ATA in the ICU. The second dive will be administered at least 8 hours following the first dive. Subsequent dives will be administered at 12 hour intervals (+/- 2 hours) for a maximum of 10 dives or until the subject is following commands or determined to be brain dead. The time intervals are defined as from the start of the one dive to the start of the next dive. The first dive of the study should be

started within 8 hours of presenting to the enrolling hospital.

Total Oxygen Exposure. The FDA reviewers recommended that "investigators should record the duration, mode of administration and concentration for any oxygen administration outside the treatment period". This is a beneficial suggestion. By recording the total amount of oxygen delivered in terms of OTUs, a quantitative description of the total amount of oxygen delivered will enhance safety of the study. More severely injured subjects, particularly those with direct lung injuries or acquired ventilator associated pneumonia will require an increased FiO2 between treatments. The total amount of oxygen delivered can be correlated with oxygen toxicity to the lungs and SAEs related to hyperoxia.

Transport of the Severe TBI Subject. Transport of critically ill subjects has been shown to be associated with potential AEs (Beckmann 2004, Shirley 2004). It is essential that the same level of care provided in the ICU is continued throughout subject transport (Weaver 1999). During the transport of the HOBIT subject to and from the HBO chamber and while the subject is in the HBO chamber, there will be at least one appropriately trained clinician with the subject at all times who is able to manage a ventilator and one critical care nurse present and available to address subject's clinical needs. Monitoring the ventilatory status of severe TBI subjects during transport is critical. If the subject requires mechanical ventilation with positive end expiratory pressure (PEEP) in the ICU, then a transport ventilator with PEEP or a manually-operated resuscitation bag with a PEEP valve will be used. Pulse oximetry to monitor O2 saturations and portable end tidal carbon dioxide (EtCO2) monitor are used routinely. Ideally, the HBO unit should be within or in close proximity to the ICU. This arrangement minimizes the time and the potential problems associated with transport and makes advantageous use of the experienced ICU support staff.

6.2 PREPARATION FOR STUDY INTERVENTION

6.2.1 PREPARATION

Assessing Subject's Ability to Tolerate Transport and HBO Treatment

It is critical that any hemodynamic, pulmonary or intracranial instability occurring in a subject prior to HBO treatment be thoroughly assessed and stabilized prior to consideration of transport to the HBO chamber. This is particularly critical prior to the first treatment occurring within several hours of admission to the hospital. It should be emphasized that these issues are intrinsic to the severity of the injury the subject has sustained both to the brain as well as to other regions of the body. The Clinical Standardization Guidelines presented in the manual of procedures are state-of-the-art and will be adhered to and monitored closely. All major intracranial procedures such as evacuation of mass lesions and/or decompressive craniectomy, or thoracotomy, or laparotomy for internal bleeding or injury are performed per protocol. Spine fractures must be thoroughly evaluated and appropriate management instituted. All subjects will have an external ventricular drain/intraparenchymal ICP monitor placed for

both ICP monitoring as well as treatment of intracranial hypertension by removal of Cerebrospinal fluid (CSF). Routine systemic monitoring of the subject includes continuous heart rate, blood pressure, electrocardiogram, and central venous or wedge pressures as needed.

Prior to transporting HOBIT subjects to the HBO chamber, subject's ability to tolerate transport and HBO treatment should be assessed. Assessment of subject's stability for transport to the HBO chamber should be performed within 2 hours of each scheduled HBO treatment. These assessments may be performed by any physician member of the clinical team including the neurointensivist, neurosurgeon, trauma surgeon, emergency physician in collaboration with the hyperbaric staff physician. If the physician member of the clinical team feels for any reason the subject is not stable to be transported to the hyperbaric chamber or to undergo a hyperbaric treatment, the scheduled treatment will be canceled. There will be no "make-up" HBO treatments. If a subject misses a scheduled HBO treatment(s) due to physiologic instability or other reasons, that treatment(s) will be considered missed and will not be re-scheduled. If subject's clinical condition improves, they may be considered for the next scheduled HBO treatment.

Management of subjects randomized to HBO treatment who cannot tolerate HBO treatments

Subjects randomized to one of the six HBO treatment groups but are not clinically stable enough to receive HBO treatment will receive "usual care" (no hyperoxia treatment). Usual care will be dictated by the clinical standardization guidelines.

Preparing the severe TBI subject for HBO treatment.

Cerebral O2 toxicity can potentially manifest itself as seizures. Severe TBI subjects are susceptible to seizures and all subjects will be loaded with prophylactic anticonvulsants and started on maintenance doses to achieve and maintain therapeutic levels for 7 days.

There are many details requiring special attention prior to the placement of the subject in the HBO chamber (Gossett 2010, Weaver 1999). All clinical sites expected to participate in the HOBIT Trial have trained personnel who are very cognizant of these critical procedures. The procedures include ensuring that: chest tubes are connected to a Heimlich type valve and drained passively into a sterile receptacle such as a Foley drainage bag or a sterile glove; the air from the endotracheal tube cuff is completely evacuated and replaced with sufficient normal saline to achieve an appropriate seal with a minimum pressure; gastric tubes are attached to a sputum trap or drainage bag; and, subdural Jackson-Pratt drains are securely occluded for the duration of treatment. In the monoplace chamber, all intravenous (IV) lines in use must have specialized hyperbaric tubing extensions. Each IV line requires its own pump, and only one line can be used for each penetration. IV check valves are positioned inside the chamber door on each line.

The subjects are connected to the hyperbaric ventilator at least 15 minutes prior to being pressurized in the HBO chamber. Ventilatory parameters are set and stabilized, and arterial blood gases are checked to verify that the ventilator parameters are appropriate. If secretions are present, the subject is suctioned thoroughly prior to the HBO treatment. Bilateral myringotomy is performed prior to the first HBO treatment. The myringotomy can be accomplished with an 18-gauge spinal needle in the anterior inferior quadrant of the tympanic membrane. The tympanic membrane should be checked each day to assure patency of the myringotomies. This procedure reduces middle ear barotrauma and thus avoids the painful stimulation which raises ICP (Rockswold 1992). A myringotomy will not be performed if there is blood in the external canal or otorrhea present. A hyperbaric pre-treatment checklist is maintained and all items performed and checked off prior to the subject entering the HBO chamber.

Monitoring of the Severe TBI Subject During HBO Treatment.

Subject monitoring and safety within the HBO chamber is of the utmost importance (Gossett 2010, Rockswold 1985, Weaver 1988, Weaver 1999, Weaver 1999). The hyperbaric chamber becomes an extension of the critical care environment. Routine monitoring of the subject includes continuous heart rate, blood pressure, electrocardiogram, and central venous pressures as needed. Intracranial monitoring, including ICP will continue throughout the HBO treatment. Brain tissue PO2 and brain temperature monitoring will be optional. ICP will be monitored using an intraventricular catheter or parenchymal monitor . If the subject has an intraventricular catheter and in a monoplace chamber, a pressure transducer is connected to the ventriculostomy line inside the HBO chamber. CSF is allowed to flow from the ventriculostomy to the transducer which converts the fluid pressure to a digital signal. This signal is transmitted through the chamber door to the outside monitors via electrical penetrations. A system will allow the attendant on the outside of the monoplace chamber to turn the ventriculostomy stopcock valve either open for draining (if ICP is elevated) or closed for intermittent ICP monitoring.

Management of the Severe TBI Subject in the HBO Chamber Monoplace Chamber

Adequate mechanical ventilation throughout the hyperbaric treatment is essential for TBI subjects with severe injury (Gossett 2010). Monoplace ventilators are generally kept on the outside of the chamber. The monoplace ventilator has to overcome the pressure differential between the outside and the inside of the chamber in order to properly ventilate the subject. A common problem with monoplace ventilators is that at any set tidal volume the delivered tidal volume decreases during compression and increases during decompression (Weaver 1988, Weaver 1999). This fluctuation is because the volume of gas changes inversely with pressure (Boyle's Law V=1/P). Therefore, respiratory rate, tidal volume, inspiratory to expiratory ratio, and peak inspiratory pressures is monitored closely throughout the hyperbaric treatment with particular vigilance during pressure changes. There will be an appropriately trained clinician responsible for ventilatory management present at all times during the hyperbaric treatment.

There are special requirements for delivering IV fluids and medications to a subject in the monoplace chamber. In a monoplace chamber, IV fluids which are delivered to the subject through the chamber door are significantly decreased during compression in the chamber. This decrease is particularly true at slow rates of IV delivery (Ray 2000, Weaver 2005). Using hard pressure tubing between the IV pump and the chamber hatch allows more rapid stabilization of the IV delivery rate at treatment pressure. During decompression, there is a potential of increased IV drip. This situation is obviated by hand administering the drug during compression and slowing the drip during decompression. High pressure IV pumps permit the controlled delivery of IV fluids.

Proper sedation or paralysis is important for proper control of the subject in the monoplace

chamber. Most severe TBI subjects are sedated as a routine part of their ICP management. Elevated ICP or a decrease in cerebral perfusion pressure (CPP) is treated during HBO in standard fashion. This treatment includes CSF drainage and administration of osmotic therapy or moderate hyperventilation. Blood pressure is supported with appropriate vascular volume expansion and/or vasopressors.

Multiplace Chambers

The ventilator in the case of the multiplace chamber is inside the chamber during treatment. Respiratory function is monitored as described for the monoplace chamber. Ventilator settings are verified with blood gases prior to initiating treatment and rechecked as needed during treatment. There will be an appropriately trained clinician responsible for ventilatory management present at all times during the hyperbaric treatment. Administration of IV fluids and medications present no special problem inside the multiplace chamber. ICP and sedation management in the multiplace is accomplished without modification of ICU protocols.

Personnel Safety

Medical personnel are not exposed to hyperbaric conditions when a monoplace chamber is utilized. In the case of the sites using multiplace chambers, all medical personnel who will attend to the subjects in the multiplace chamber must undergo medical clearance according to the standards of the Undersea and Hyperbaric Medical Society (UHMS).

The various HBO treatment paradigms to be evaluated in the HOBIT trial are well within the normal limits of HBO treatments utilized for standard indications.

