1.2 SCHEMA

1.3 DATA COLLECTION SCHEDULE

	1		1	-		-	-				Day 30	Day 90	Day 180	
Form #	CRF	Baseline	Randomization	Day 1	Day 2	Day 3	Day 4	Day 5	Day 6	Ho spital				End of
				,-	,-	,-	, -	, -	,-	Discharge	+/· 7 days	+/- 14 days	†√-21days	Study
N/A	Subject Enrollment	x												
F138	Glasgow Coma Scale	XM		XM	XM	XM	XM	XM	XM					
F101	Inclusion and Exclusion Criteria	XM												
F102	Randomization		x											
F105	Medical History	х												
F274	Pre-hos pital Events	х												
F285	Pupil Reactivity	х		х	X	х	X	X	х					
F117	Vital Signs	х												
F105	Laboratory Tests	х		х	X	х	X	X	х					
F271	CT Scan	х		х										
F272	CT Scan - Central Reader	х		х										
F501	Hourly Monitoring			XM	XM	XM	XM	XM	XM					
F275	Study Therapy			XRM ^{C1}	ORM ⁶¹									
F287	Therapy Intensity Level Scale			Х	X	Х	X	X	Х					
F502	Ventilatory Parameters			XM	XM	XM	ХМ	XM	ХМ					
F112	Concomitant Medications			х	X	х	х	X	х					
F172	Surgical and Procedural Interventions									х				
F123	Hospital Discharge									XM				
F156	Glasgow Outcome Scale - Extended										XM	XM	XM	
F104	Adverse Event			OR	OR	OR	OR	OR	OR	OR	OR	OR	OR	
F127	MedWatch			XR ^{C2}	XR ^G	XR ^{C2}	XR ^{C2}	XR ^{C2}	XR ^G	XR ^{C2}	XR ^{C2}	XR ^{C2}	XR ^{Gr}	
F126	End of Study													XM
F269	Abbreviated Injury Scale													х

X = Required O = Optional R = Repeatable C1 = Non control subjects C2 = MedWatch is required per IMSM

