Critical hypotension (MAP<70 mmHg)	This AE is not specific to HBO therapy, but related to transfer from critical care unit (e.g. disconnecting and reconnecting of lines). It is expected to be the same in all groups but could demonstrate differences if the process of transferring to the dive chamber causes increased AEs. This should be analyzed as active vs. control.
Seizures during HBO treatment	These are expected to occur immediately proximal to treatment as a function of dose oxygen toxicity (rather than cumulative exposure). It is possible to have multiple episodes of AE. Subjects with a baseline propensity to seize may elevate the numerator for this AE.

Hypercarbia during transportation (PaCO2>45 mmHg)	This AE is not specific to HBO therapy, but related to transfer from critical care unit (e.g. disconnecting and reconnecting of lines). It is expected to be the same in all groups but could demonstrate differences if the process of transferring to the dive chamber causes increased AEs. This should be analyzed as active vs. control.
---	---

All AEs and SAEs are summarized by preferred term and associated system-organ class according to the MedDRA adverse reaction dictionary and by treatment group in terms of frequency of the event, number of subjects having the event, time relative to randomization, severity, and relatedness to the treatment. Cumulative incidences of the specific SAEs related to HBO, as well as all SAEs, will be compared across arms. Additional evaluation of safety events will be conducted adjusting for relative baseline co-variants, such as age at baseline and GCS score.

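### Blood gases are built into pre-dive preparation in the HBO arms only, so pulmonary dysfunction can be found more often in HBO than in control or NBH-only subjects without any lung toxicity

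*Protocol*

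**What the plan says.** **Gases in the HBO arms.** Section 6.2.1 describes connection to the hyperbaric ventilator before pressurization and continues: "Ventilatory parameters are set and stabilized, and arterial blood gases are checked to verify that the ventilator parameters are appropriate". The multiplace text of the same section says: "Ventilator settings are verified with blood gases prior to initiating treatment and rechecked as needed during treatment". Neither sentence uses the word each. Since the gas verifies ventilator settings before treatment starts, once per dive is a fair reading. Section 6.1.2 sets the number: "Subsequent dives will be administered at 12 hour intervals (+/- 2 hours) for a maximum of 10 dives".

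**Gases in the other arms.** No matching step is written for control. For NBH-only, Section 6.1.2 says: "The NBH without HBO treatment arm will likewise be ventilated with 100% O2 for 4.5 hours at 1.0 ATA in the ICU", with no gas attached. The schedule in Section 1.3 does require Laboratory Tests and "Ventilatory Parameters" on Days 1 to 6 without limiting them to active arms; only Study Therapy carries the non-control footnote. The contents of those forms are not stated.

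**The event.** The Section 3 table lists pulmonary dysfunction among the SAEs as a P/F ratio below 200. Section 9.4 defines it as P/F at or below 200, or PEEP above 10 cm of water needed to keep the ratio above 200. Neither says which reading counts or whether a low value must persist.

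**The comparison.** Section 9.4: "Cumulative incidences of the specific SAEs related to HBO, as well as all SAEs, will be compared across arms".

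**The concern.** A cumulative incidence based on a threshold grows with the number of times the quantity is measured. If one group has up to 10 protocol-driven measurements that the others lack, its incidence can be higher when the underlying lung function is identical.

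Two comparisons are exposed: HBO against control, and HBO against NBH-only. The second matters because Section 4.1 gives the NBH arm the role of a control for pressure, and Section 2.3.3 names oxygen toxicity as its only added risk. An artificial pulmonary excess in HBO would look like an effect of pressure. Section 9.4 also expects true pulmonary toxicity to rise with the number of treatments. Pre-dive gases rise with the number of dives too, so unequal measurement can imitate the pattern that reviewers are told to look for.

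**Working it through.** The protocol gives no event rate, gas count or power for this outcome, so there is no figure to reproduce. The check asks what the plan yields when no arm has any lung toxicity.

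**Inputs from the protocol.** Up to 10 dives (6.1.2); one gas per dive (inferred from 6.2.1); Days 1 to 6, or 144 h, as the window (1.3, 8.4.4).

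**Assumed inputs.** Chance p that a single reading is at or below 200: 2% to 10%. Background gases in every arm every 24, 12 or 6 h, so k = 6, 12 or 24 readings.

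**Step 1, independent readings.** Chance of at least one low reading = 1 − (1 − p)^k without dives and 1 − (1 − p)^(k+10) with ten.

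| p | Background | No dives | Ten dives |
|---|---|---|---|
| 0.02 | daily (k = 6) | 11.4% | 27.6% |
| 0.02 | 6-hourly (k = 24) | 38.4% | 49.7% |
| 0.05 | daily (k = 6) | 26.5% | 56.0% |
| 0.05 | 12-hourly (k = 12) | 46.0% | 67.6% |
| 0.05 | 6-hourly (k = 24) | 70.8% | 82.5% |

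Ten dives is the maximum. With five and daily background gases, 1 − 0.98^11 = 19.9% (against 11.4%) and 1 − 0.95^11 = 43.1% (against 26.5%).

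**Step 2, correlated readings.** Independence exaggerates the effect, because a low P/F tends to last. A latent Gaussian process was simulated hourly over 144 h for 40,000 subjects, with p = 5% or 10%, a correlation time of 6 or 24 h, and a between-subject share of variance of 0 or 0.5. It was read on the background schedule alone, or with ten pre-dive readings added (one of which coincides with a 12-hourly reading). The last column is the chance of a two-sided 5% signal for an assumed 40 control and 120 HBO subjects; the actual split depends on adaptive allocation.

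| Background gases | Risk ratio, HBO v no dives | Difference | Chance of a false signal |
|---|---|---|---|
| daily | 1.25 to 1.89 | 6 to 28 points | about 10% to 89% |
| 12-hourly | 1.11 to 1.34 | 3 to 15 points | about 5% to 44% |
| 6-hourly | 1.03 to 1.09 | 1 to 6 points | about 3% to 11% |

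**Step 3, common times.** If the event is derived from the same reading times in all arms, the no-toxicity difference is zero by construction.

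**Step 4, does ICP behave the same way?** ICP is recorded every 15 minutes around dives (6.1.2), and "F501 Hourly Monitoring" applies to all arms (1.3). Assume 15% of time above 22 mmHg, the same process inside and outside the chamber, and 2 h of 15-minute readings per dive over 120 h. Readings rise from 120 to 180. The share above 22 stays at 14.9% and the time-weighted duration at 17.9 h. Only the raw count of high readings (17.9 v 26.8) and, slightly, the chance of any high reading (92.6% v 93.6%) change.

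**The case against.** **Gases are collected in all arms.** A reader might infer that control and NBH-only subjects have no measurement schedule. The documents do not support that: Section 1.3 requires laboratory and ventilator forms in every arm on Days 1 to 6. What is missing is narrower, namely whether those forms hold PaO2 and FiO2 and whether only those readings define the event.

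**A pre-dive gas need not become an event.** It serves to check ventilator settings, and the log items listed in Section 6.4 do not include it. Seriousness is judged clinically (8.4.2) and reviewed by the medical safety monitor (10.1.4), and Section 9.4 looks for new onset or worsening. These filters would reduce the effect. They do not remove it, because Section 3 lists the P/F threshold itself among the SAEs, all AEs are reportable through Day 6 or discharge (8.4.4), and no text excludes readings taken before a dive.

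**Fewer than ten extra gases.** Dives end early in subjects who recover or are declared brain dead, and are cancelled without replacement in unstable ones. A pre-dive gas may also replace a clinical one. Both points stand, so results at ten dives are the upper end.

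**Dose comparisons.** A reader might infer that the comparison of lung toxicity by HBO dose is biased. It has no built-in imbalance: all six HBO arms share the same dive schedule and gas checks.

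**ICP and brain tissue PO2.** A reader might infer that the 15-minute chamber readings bias these endpoints likewise. The endpoints are level and duration, the derivation is left to the SAP, and denser sampling does not bias a time-weighted duration (Step 4). An unweighted count of readings would be affected, but the protocol proposes none.

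**Conclusion.** The concern holds for pulmonary dysfunction in HBO v control and HBO v NBH-only. The protocol ties extra gases to dives and compares, as cumulative incidence, an event that depends on how often gases are drawn. A spurious excess is possible, not certain. Under the assumed correlated readings with ten dives it ranges from material (risk ratio 1.25 to 1.89, daily background gases) to negligible (1.03 to 1.09, 6-hourly). The background frequency that decides between these is not in the protocol; usual care follows guidelines in a manual that is not shown. The per-reading probabilities, the correlations and the 40 v 120 split are assumptions.

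The documents do not support extending the point to contrasts among HBO doses or to the ICP and brain tissue PO2 endpoints. The two definitions of pulmonary dysfunction, in Sections 3 and 9.4, do conflict.

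**What to change.** 1. For the between-arm comparison of pulmonary dysfunction, derive the event from blood gases at the same scheduled times in every arm, for example those on the Day 1 to 6 Laboratory Tests and Ventilatory Parameters forms, after confirming that the forms capture PaO2 and FiO2.
2. Keep every event, including those found on pre-dive or in-dive gases, in the full AE and SAE tables and the DSMB listing, reported alongside the common-schedule comparison.
3. Reconcile the definitions of pulmonary dysfunction in Sections 3 and 9.4.
4. Optionally, state that ICP and brain tissue PO2 level and duration are time-weighted or taken on the hourly grid. Keep the chamber readings, which the secondary endpoint on peak brain tissue PO2 during HBO needs.
5. As an editorial matter, correct the Section 6.1.2 sentence "For all randomized subjects, ICP will be monitored during HBO treatments and ICP will be recorded every 15 minutes", which cannot apply to control or NBH-only subjects because they have no HBO treatments.

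The cost is one more derivation and some wording, provided the forms hold the needed values; if they do not, a form change is required. Events seen only on a pre-dive gas will not count in the common-schedule comparison, which is why the full tables must stand beside it.
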